5.5.5 Permitted dose adjustments and interruptions of study treatment

For all everolimus subjects who are unable to tolerate the protocol-specified dosing schedule, dose adjustments are permitted in order to keep the subject on investigational drug. The following guidelines should be followed (Table 5-2), for management of lipid elevations refer to Section 5.5.7 for initial approach, prior to considering dose reduction. The everolimus dose should be decreased by at least 0.25 mg b.i.d if a dose reduction is necessary. If a temporary reduction in everolimus level is needed, the everolimus trough blood level should still be maintained no lower than 3 ng/mL. Everolimus should be discontinued if a trough level \geq 3 ng/mL cannot be maintained due to toxicity. Severe and unremitting changes may also lead to investigational drug discontinuation.

For subjects having rATG administered, whether as induction therapy, DGF or anti-rejection treatment the relative impact of all medications to reduced hematological parameters should be considered, thus everolimus dose reduction to these guidelines may not always be necessary under these circumstances.

Table 5-2 Guidelines for everolimus dose reduction/interruption

	Platelet count (/mm³)	Hemoglobin (g/dL)	WBC count (/mm³)	Cholesterol (mmol/L)	Triglycerides (mmol/L)
Dose reduction	≤ 75000	≤ 8	≤ 3000	> 9	> 8.5
Interruption	≤ 50000	≤ 6	≤ 2500	≥ 10	≥ 10.5

If everolimus is interrupted for safety reasons for longer than 21 consecutive days study regimen should be discontinued. Everolimus may be interrupted during antibody treatment of rejection episodes. In case of any planned or emergency surgery during the study treatment period, everolimus can be interrupted and a compensatory increase in CNI may be considered. In elective cases, this may be done 5 days before surgery which would allow restart of everolimus by 21 days post-surgery, in these cases everolimus must be re-introduced at the latest by day 27 after discontinuation.

For MPA, dose adjustment or interruption should follow Appendix 3. If MPA or either CNI is interrupted for more than 21 consecutive days the randomized study regimen must be discontinued. Subjects who discontinue their randomized study regimen are expected to remain in study with immunosuppression according to local practice until completing the treatment period at Month 24, visits and assessments for such subjects are described in Table 6-1. All immunosuppressive therapy administered post discontinuation of study regimen (i.e.

MPA+CNI or EVR+CNI) should be recorded on the concomitant Medications CRF under the immunosuppressive category.

For subjects having rATG administered, whether as induction therapy, DGF or anti-rejection treatment the relative impact of all medications to reduced hematological parameters should be considered, thus MPA dose reduction may not always be necessary under these circumstances.

All dose changes must be recorded on the everolimus or MPA Dosage Administration Record CRF as appropriate.

Treatment of Acute Rejection episodes

In all suspected acute rejection episodes, regardless of initiation of anti-rejection treatment, an allograft biopsy must be performed within 48 hr. All episodes of acute rejection must be entered on the corresponding CRF (e.g. Acute Rejection CRF, Kidney Allograft Biopsy CRF, etc.) preferably within 24 hr.

Acute rejections should be treated with bolus methylprednisolone (other corticosteroids are acceptable at an equivalent dose) according to local practice. Recommended treatment is with at least 3 boluses of i.v. methylprednisolone with a minimal dose of 250 mg/bolus or at least 2 boluses of i.v. methylprednisolone with a minimal total dose of 750 mg.

Other anti-rejection therapies (i.e. antibody therapy) should only be used in cases of steroidresistant rejections, vascular rejections or rejections with a Banff grade $\geq 2B$.

All medications used for the treatment of suspected or confirmed acute rejections must be recorded on the Concomitant Medications CRF under the Immunosuppressive category.

Treatment of Delayed Graft Function (DGF)

In case of DGF, treatment will be according to local practice, but the randomized study regimen cannot be interrupted for more than 21 consecutive days. DGF treatments must maintain sufficient immunological coverage for the graft and may include maintaining, interrupting or reducing the dose of CNI and the use of anti-thymocyte globulin. In case of use of depleting antibody hematological parameters (e.g. lymphocytes, WBC and platelets) must be monitored carefully. Use of MPA and everolimus in subjects randomized to the other treatment arm (i.e. everolimus or MPA respectively) is prohibited during any interruption whether for DGF or other reasons

If a subject with DGF is not able to return to or maintain their randomized study regimen as per protocol after 21 consecutive days of interruption, the subject should be discontinued from the study. If a subject is placed on permanent dialysis (or retransplanted) the Graft Loss, and Adverse Event CRFs should be completed, as well as an SAE report of Graft Loss submitted. Dialysis treatments should be recorded on the Dialysis CRF. Retransplantation should be recorded on the surgical and medical procedures CRF.

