5.5.9 Discontinuation of study treatment and discontinuation from study

Discontinuation of study regimen

The Dosage administration records for everolimus, MPA, tacrolimus and cyclosporine will be used to record if a subject has permanently discontinued study treatment and why.

Possible reasons for study treatment discontinuation are:

- Adverse Event
- Lack of Efficacy
- Technical problems
- Subject/Guardian Decision
- Lost to follow-up
- Death
- Graft Loss

The investigator should discontinue a subject from their randomized treatment regimen if, on balance, he/she believes that continuation would be detrimental to the subject's well-being.

If, at any time throughout the study, the randomized treatment regimen or any component of the regimen is interrupted for longer than 21 consecutive days, unless being held due to an elective surgical procedure then study regimen should be discontinued.

Subjects who become pregnant while taking study medication must be discontinued from study medication and from the study, such pregnancies should be reported as SAEs to Novartis DSE and entered as AEs in the CRF, the reason for discontinuation of study medication should be recorded as AE and reason for discontinuation from study is pregnancy (see next section below).

Subjects who discontinue their randomized study regimen (any component whether everolimus, MPA or the CNI) should remain in the study, if possible, and receive standard of care immunosuppression, according to local practice, until completing the study at Month 24. Visits and assessments for such subjects are described in Table 6-1. All immunosuppressants after

discontinuation of study regimen must be recorded on the Concomitant Medication CRF under the Immunosuppressive category.

Subjects are expected to remain on the original CNI (combined with everolimus or MPA) to which they were randomized until at least Month 24. However, if subjects discontinue either CNI due to AE/tolerability and maintain everolimus or MPA combined with the alternate CNI, administered to respective target levels per protocol, they will not be considered to have discontinued study regimen/medication.

Discontinuation from Study and Study/Period completion

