Subjects who discontinue their study treatment regimen should NOT be considered withdrawn from the study. Such subjects should remain in the study, if possible, and receive standard of care immunosuppression, according to local practice, until completing the study at Month 24. See Table 6-1 for the required assessments of these subjects after discontinuation of study regimen.

The status of every randomized subject must be recorded on Month 12 and/or Month 24 Study Phase Completion CRFs as either completing or discontinuing from the respective study period, with reason for discontinuation.

Possible reasons for discontinuation from the study are:

- Technical problems
- Subject/Guardian Decision
- Lost to follow-up
- Death
- **Graft Loss**
- Study terminated by sponsor
- Pregnancy

Subjects may voluntarily withdraw from the study for any reason at any time. They may be considered withdrawn if they state an intention to withdraw, fail to return for visits, or become lost to follow-up for any other reason.

If premature withdrawal occurs for any reason, the investigator must make every effort to determine the primary reason for a subject's premature withdrawal from the study and record this information on the Study Phase Completion CRF at Month 12 and/or Month 24 as applicable.

For subjects who are lost to follow-up (i.e. those subjects whose status is unclear because they fail to appear for study visits without stating an intention to withdraw), the investigator must show "due diligence" by documenting in the source documents steps taken to contact the subject, e.g. dates of telephone calls, registered letters, etc.

Subjects who are prematurely withdrawn from the study will not be replaced.

5.5.10 **Emergency breaking of treatment assignment**

Not applicable.

Study completion and post-study treatment 5.5.11

Subject who successfully complete 24 months on treatment may be eligible to participate in a separate observational extension study for a further three years. Subjects who are prematurely withdrawn from the study should be treated according to local standard of c are per investigator's judgment.

The study will be complete and ready for final analysis when the last active subject has completed their Month 24 visit.

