regimen prescribed should be recorded on the Concomitant medication CRF under the immunosuppressive category and any CNI trough levels should be recorded on the appropriate local lab trough CRF.

For subjects who have discontinued randomized study regimen, visits need only be completed at Months 6, 9, 12, 18 and 24. For all subjects completing the study to Month 12 or discontinuing from the study prior to Month 12, the M12 Period completion form should be completed, regardless of on or off-treatment status. Similarly post-Month 12, for all subjects completing the study to Month 24 or discontinuing from the study prior to Month 24, the M24 Period completion form should be completed, regardless of on or off-treatment status.

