9.4.3 Handling of missing values/censoring/discontinuations

Since the subjects who have prematurely discontinued study regimen are followed on standard of care, renal function data (e.g. creatinine) and kidney allograft biopsy data will be collected post discontinuation of study regimen for these visits, it is expected that few subjects would be missing efficacy and/or renal function evaluation for the 12 month analysis.

To define the primary variable – composite endpoint of tBPAR or eGFR (MDRD4) < 50 mL/min/1.73m², the following imputation method will be applied for subjects with missing 12month eGFR value. As allograft biopsy data will be collected on an as needed basis due to the nature of kidney transplant studies, no particular rule for missing biopsy will be applied.

- Under the assumption of missing not at random (MNAR), subjects who lost their grafts will be assigned a value of zero for their 12-month eGFR;
- Otherwise, under the assumption of missing at random (MAR), subjects who had missing values including those who died with a functioning graft will have a 12-month eGFR imputed using multiple imputation method based on the longitudinal eGFR (MDRD4) data at all available time points and covariates of randomization strata (donor type and CNI), HLA mismatches ($\leq 3 \text{ vs} > 3$) and induction.

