9.5 Analysis of secondary variables

9.5.1 Assessment of the key secondary endpoint of tBPAR, graft loss, or death

For the key secondary objective regarding the composite efficacy failure of tBPAR, graft loss or death, to evaluate whether everolimus plus reduced CNI is non-inferior to MPA plus standard CNI at 12 months post-transplantation, the following hypotheses will be evaluated (α =0.025, one-sided) based on the Full Analysis Set:

The null hypothesis:

 H_{03} : $R_{EVR+rCNI}$ - $R_{MPA+sCNI} \ge 0.10$ (non-inferiority margin): the difference in Kaplan-Meier event rate of the composite efficacy failure of tBPAR, graft loss or death at 12 months between the everolimus plus reduced CNI ($R_{EVR+rCNI}$) and the MPA plus standard CNI arm ($R_{MPA+sCNI}$) is at least 10%.

The alternative hypothesis:

 H_{A3} : $R_{EVR+rCNI}$ - $R_{MPA+sCNI}$ < 0.10 (non-inferiority margin): the difference in Kaplan-Meier event rate of the composite efficacy failure of tBPAR, graft loss or death at 12 months between the everolimus plus reduced CNI ($R_{EVR+rCNI}$) and the MPA plus standard CNI arm ($R_{MPA+sCNI}$) is less than 10%.

For this analysis, the event rate of the composite efficacy failure of tBPAR, graft loss or death will be estimated with Kaplan-Meier product-limit formula. Greenwood's formula will be used to estimate variance of failure rates and to derive Z-test based confidence interval for the difference in failure rate between the everolimus plus reduced CNI and the MPA plus standard CNI arm.

Since the subjects who have prematurely discontinued study regimen are followed on standard of care, efficacy data including kidney allograft biopsies will be collected post-discontinuation of study regimen for these visits, it is expected that few subjects would be missing efficacy evaluation for the 12 months analysis. Subjects with missing efficacy evaluation for the 12 month analysis will be censored at the latest day known to be free of the event.

As supportive analyses, this non-inferiority analysis will be repeated using the Per-Protocol Set, and Kaplan-Meier event rates of this key secondary endpoint will be summarized for the subgroups defined in Section 9.4.4.

Novartis Confidential Page 54
Amended Protocol Version v01 Clean Protocol No. CRAD001A2433

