## 4.2 Missing Data Handling

### 4.2.1 Missing GFR Data Imputation

#### 4.2.1.1 Main Imputation

The following is the main imputation method for handling missing eGFR data at Month 12. A similar imputation rule can be applied for missing eGFR at Month 24. These imputations will be applied to the primary analyses for the composite endpoint of tBPAR or eGFR < 50 mL/min/1.73m^2, as well as for eGFR alone. For the component of eGFR < 50 mL/min/1.73m^2, a value for missing eGFR as a continuous variable will be imputed first, then it will be dichotomized in order to derive this endpoint.

- Under the assumption of missing not at random (MNAR), patients who lost their grafts will be assigned a value of zero for their missing eGFR at the visits on and after graft loss;
- Multiple imputation: Otherwise, under the assumption of missing at random (MAR), patients who had missing values including those who died with a functioning graft will have a 12-month eGFR imputed using multiple imputation method based on the covariates/factors CNI, region, donor type, HLA mismatch ( $\leq 3$  vs  $> 3$ ), induction therapy, recipient gender, recipient age, donor age, and DGF, and all eGFR (MDRD4) data collected at the visit windows during the analysis period of interest. In the multiple imputation, recipient age, donor age and eGFR (MDRD4) data will be treated as continuous variables. To help preserve the relationship between outcome and covariates within each treatment, a separate model will be run for each treatment. This will also help ensure that the imputation model does not make stronger assumptions on data relations than the analysis model.

To ensure that results can be replicated, the data should be sorted by patient number before running the model (the data should be in horizontal format with one row per patient). If there are multiple renal function assessments within a visit window, guidelines given in [Section 2.1](#) will be followed, i.e., the closest value to the planned visit (midpoint of visit window for post-baseline visits) will be taken (if tie, the last will be used) for imputation. In addition, the seed used in the multiple imputation will be 2433.

See dummy SAS codes below.

```
proc mi data=DATAIN out=DATAOUT nimpute=100 seed=2433;
  by treatment;
  class CNI region donor HLA induction gender_r DGF;
```

```
fcs reg (/details);  
var CNI region donor HLA induction gender_r age_r age_d DGF GFR_vis1  
GFR_VIS2 ... GFR_VISm;  
run;

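### The delayed graft function paragraph takes subjects out of the study after 21 days off regimen, while the rest of the protocol stops only the regimen and keeps follow-up to Month 24

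*Protocol*

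**What the plan says.** The DGF paragraph of Protocol Section 5.5.5 allows local management of DGF, including interruption of the CNI, but limits interruption of the regimen to 21 consecutive days. For a subject who cannot then return to the regimen or stay on it, it states that "after 21 consecutive days of interruption, the subject should be discontinued from the study". Permanent dialysis and retransplantation are dealt with in the next sentence, so this one also covers subjects whose graft has not been recorded as lost.

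Elsewhere the protocol treats the same trigger differently:

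- Section 5.5.9, on interruption of any component for longer than 21 consecutive days: "unless being held due to an elective surgical procedure then study regimen should be discontinued".
- Section 5.5.5, after the 21-day rule for MPA and CNI: "Subjects who discontinue their randomized study regimen are expected to remain in study with immunosuppression according to local practice".
- Section 5.5.9, on leaving the study: "Subjects who discontinue their study treatment regimen should NOT be considered withdrawn from the study".
- Notes to Table 6-1: "For subjects who have discontinued randomized study regimen, visits need only be completed at Months 6, 9, 12, 18 and 24".

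The glossary defines treatment discontinuation and study discontinuation as separate events. The reasons for leaving the study listed in Section 5.5.9 include neither DGF nor prolonged interruption. Pregnancy is the only stated case in which a subject with a functioning graft must leave the study.

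**The concern.** By the glossary's own definition, leaving the study ends participation. A literal reading would therefore stop data collection a few weeks after transplant in subjects chosen because their graft started badly and they could not resume treatment.

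Subjects with recorded graft loss are not the problem, because their eGFR is set to zero. The gap is subjects removed before any graft loss is recorded:

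- **Primary endpoint.** Under SAP Section 4.2.1.1 such a subject "will have a 12-month eGFR imputed using multiple imputation method based on the covariates/factors CNI" and other baseline factors including DGF, under a missing-at-random assumption, from at most a few early eGFR values. Rejection after exit would be unseen, and Protocol Section 9.4.3 applies no rule for missing biopsies.
- **Key secondary endpoint.** Protocol Section 9.5.1: "Subjects with missing efficacy evaluation for the 12 month analysis will be censored at the latest day known to be free of the event". Censoring at a DGF-driven exit may well be informative.
- **Missing-data premise.** Section 9.4.3 argues that "it is expected that few subjects would be missing efficacy and/or renal function evaluation for the 12 month analysis" because subjects off the regimen are still followed. The DGF sentence removes that follow-up for this group.

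DGF is also a prespecified subgroup for the primary endpoint (SAP Sections 2.2.1 and 2.5.4.3), and the loss would be concentrated there.

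**Working it through.** **1. The texts side by side**

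| Place in protocol | Trigger | Action |
|---|---|---|
| 5.5.4, tacrolimus and cyclosporine | CNI stopped more than 21 days | Switch CNI or stop regimen; stay in study |
| 5.5.5, everolimus | Interrupted more than 21 days for safety | Stop regimen |
| 5.5.5, MPA or CNI | Interrupted more than 21 days | Stop regimen; stay in study to Month 24 |
| 5.5.9 | Any component interrupted more than 21 days, elective surgery excepted | Stop regimen; stay in study to Month 24 |
| 5.5.5, DGF | Cannot resume or maintain regimen after 21 days of interruption | Leave the study |

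One patient can fall under two rows. A DGF subject whose CNI is held for more than 21 days is kept in the study by the third row and removed by the last. No text says which rule prevails.

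**2. Power is not the issue**

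Inputs from Protocol Section 9.7: 1020 per arm, 50% event rate in each arm, 10-point margin, one-sided 0.025.

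- Plan's figure: power = Φ(0.10/√(2 × 0.5 × 0.5/1020) − 1.96) = Φ(4.517 − 1.960) = 99.5%. Table 9-1 states above 99%, so it is reproduced.
- With 5% of each arm lost outright (969 per arm), power is 99.3%.

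What matters is selective missingness.

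**3. Illustrative bias in the primary difference**

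The documents give neither the number removed nor the failure probabilities, so two inputs are assumed: the removals per arm, and a gap of 0.20 to 0.35 by which imputation understates the failure probability of those removed.

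Net bias = (removed in everolimus arm − removed in MPA arm) × gap / 1020

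At the margin (60% against 50%): SE = √(0.6 × 0.4/1020 + 0.5 × 0.5/1020) = 0.0219, or 2.19 points.

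One-sided type I error = Φ(−1.96 + bias/SE) if the everolimus arm loses more, and Φ(−1.96 − bias/SE) if the MPA arm loses more.

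| Removals | Gap | Size of bias (points) | Type I error, everolimus loses more | Type I error, MPA loses more |
|---|---|---|---|---|
| Equal | Any, same in both arms | 0 | 2.5% | 2.5% |
| 20 vs 10 | 0.20 | 0.20 | 3.1% | 2.0% |
| 20 vs 10 | 0.35 | 0.34 | 3.6% | 1.7% |
| 30 vs 10 | 0.20 | 0.39 | 3.7% | 1.6% |
| 30 vs 10 | 0.35 | 0.69 | 5.0% | 1.2% |

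A 1-point bias would need an imbalance of 0.01 × 1020/0.35 = 29 to 0.01 × 1020/0.20 = 51 subjects. Extra variance from multiple imputation is ignored.

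**4. A second set of assumptions**

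If the share removed differs by 1 to 3 percentage points between arms and the gap is 10 to 30 points, the bias runs from 0.01 × 10 = 0.1 to 0.03 × 30 = 0.9 points. The order of magnitude is the same.

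**The case against.** The sentence is probably a drafting slip. The surrounding 21-day rules stop only the regimen, Section 5.5.9 says off-regimen subjects are not withdrawn, and Section 6 expects every randomized subject to continue to Month 24. A site would have to set those aside and pick an exit reason that does not fit. The group is narrow: DGF, a long interruption, failure to resume, no recorded graft loss, and a site following this sentence over the others. Nothing in the documents shows that anyone was removed. The removal counts and the gap are invented, and the 5.0% figure needs a 3:1 imbalance, the larger gap and a true effect exactly at the margin. The SAP also has safeguards: DGF, donor type and donor age enter an imputation model fitted by arm, and the primary tests are repeated under control-based imputation (Sections 2.5.4.4 and 4.2.1.2). Finally, Amendment 1 reports 2037 subjects already randomized of about 2040 planned, so new wording would protect almost nobody.

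Much of this stands. The size is small and conditional, a slip is plausible, and rewording alone comes late. The conflict itself is not answered. The DGF sentence is the more specific rule, so a site could reasonably follow it. The safeguards are partial: control-based imputation recovers no lost data and leaves the MPA arm under missing at random. The composite that counts loss to follow-up as failure (SAP Sections 2.7.1 and 4.3.9) does not cover the primary endpoint.

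**Conclusion.** The concern holds. The protocol gives two incompatible instructions for the same event, and one of them ends Month 12 follow-up for a prognostically selected group. Confidence is high on the contradiction; its practical effect is unknown, because the documents do not say how many subjects left under this sentence.

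Under the assumptions shown, the shift in the primary difference is below 1 point against a 10-point margin. It is zero if removal and imputation error are the same in both arms. Unequal removal is possible in an open-label trial whose interruption thresholds differ by arm (for white cell count, 2500/mm³ or below for everolimus, below 2000/mm³ mandatory for MPA), but its direction cannot be predicted. This should be corrected; it does not threaten the design or, on these figures, the main conclusion.

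**What to change.** 1. In the DGF paragraph of Section 5.5.5, state that the subject stops the randomized regimen and is followed to Month 24 under the assessments marked X in Table 6-1. This changes one phrase and uses an existing schedule.
2. Because nearly all subjects were randomized by Amendment 1, write to sites asking whether anyone was withdrawn under this sentence. Where consent permits, retrieve Month 12 creatinine, graft status and vital status.
3. Report the number withdrawn this way by arm. The Section 5.5.9 exit reasons would not reveal it, so the count must come from the sites. If it is zero, the matter closes.
4. If any remain without Month 12 data, add one sensitivity analysis scoring them as failures on the primary endpoint.

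The cost is a wording change, one site letter, limited data retrieval and at most one extra table. No design figure changes.
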